5.12. Postdiscontinuation Therapies

The numbers and percentages of patients reporting postdiscontinuation therapies will be provided overall, and by type of therapy (surgery, radiotherapy, or systemic therapy, for the Part B ITT population and for the Part C ITT population. Surgery and radiotherapy will be further characterized by intent. Systemic therapy will be further categorized by WHO drug terms.

The analyses above might be repeated for 1^{st} , 2^{nd} , \cdots , subsequent therapies.

5.13. Patient-Reported Outcome Analyses

There is no PRO analysis planned for Part A. Descriptive analyses with each PRO instrument will be performed for Parts B and C.

For each instrument, percentage compliance will be calculated as the number of completed assessments divided by the number of expected assessments (that is, patients still on study and alive). Percentage compliance will be summarized by treatment arm and overall. Reasons for noncompliance will be described.

5.13.1. Lung Cancer Symptom Scale

The LCSS assessments will be used primarily to calculate TtD for each of the 9 items, ASBI, and LCSS total score as defined in Section 5.3.3.

- The Kaplan-Meier method will be used to estimate parameters for time-to-event analyses on each treatment arm. Kaplan-Meier curves by treatment arm will be produced.
- HRs for treatment effect and their 2-tailed 95% CIs will be estimated using the Cox PH model stratified identically to the stratified log-rank tests. A Forest plot of the estimated HRs and their 95% CIs will be generated.
- The LCSS data will be summarized descriptively by baseline and cycle for actual measurement and change from baseline by treatment arm. For the LCSS (each item, ASBI and Total LCSS), maximum improvement over baseline is defined as the largest magnitude decrease from baseline. The analysis of maximum improvement will be conducted to compare the study treatment arms for each score using analysis of covariance (using only baseline score as a covariate) and the Mann-Whitney-Wilcoxon test. Percentage of patients who improved, remained stable, or worsened will be reported. Additionally, mean change from baseline will be estimated using Mixed effect Model Repeat Measurement (MMRM) regression and will include independent variables treatment, visit, treatment*visit, and baseline. A negative change will indicate improvement.

Additional exploratory analyses, including pattern mixture model as a sensitivity analysis to assess missingness, subgroup analysis, association with clinical outcomes, time to sustained deterioration, and predictive modeling, may be performed as deemed appropriate.

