5.1.2. Part B

The study will enroll approximately 450 patients in 1:1 randomization (that is, approximately 225 patients will be randomly assigned to each treatment arm). The primary PFS analysis will be performed after approximately 270 PFS (approximately 40% censoring rate) events.

An interim futility analysis was conducted at 114 investigator-assessed PFS events (data cutoff date 16 October 2017), and the IDMC recommended the trial continue without modification. A nominal 1-sided alpha <0.00001 was spent in order to maintain type-I error. Assuming an HR of 0.71, this sample size yields at least 80% statistical power to detect superiority of the ramucirumab plus erlotinib arm over the placebo plus erlotinib arm, with the use of a 1-sided log-rank test and a type I error of 0.02499. If the true median PFS for the placebo plus erlotinib arm is 11 months, then the HR of 0.71 amounts to an approximate 4.5-month improvement in median PFS for the ramucirumab plus erlotinib arm under an additional assumption of exponential survival distribution.

Sample size calculation is carried out in EAST Version 6.4 (1994-2016).

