5.2. General Considerations

Part A: The analyses for Part A will be descriptive. Data analyses will be provided separately for study patients in the 2 geographic areas: 1) Japan, 2) European Union (EU) and United States, and 3) total. The list of analyses conducted for the Assessment Committee (AC) review is included in the AC charter.

Part B: All tests of treatment effects will be conducted at a two-sided alpha level of 0.05, and all CIs will be given at a two-sided 95% level, unless otherwise stated. Statistical analysis will be performed using SAS software (SAS, Version 9.2 or higher).

Part C: This part is only applicable to sites in the East-Asian region, including Japan. The analyses for Part C will be descriptive and conducted separately from Parts A and B. Results of Part C will be included in a separate addendum to the clinical study report (CSR) for Parts A and B. Safety data of Part C will be summarized by each period. Patients who do not enter Period 2 will not be included in summary safety analyses for Period 2.

This document describes the statistical analyses planned prior to final treatment assignment unblinding of the aggregate database. Any change to the data analysis methods described in the protocol will require an amendment ONLY if it changes a principal feature of the protocol. Before unblinding of the aggregate database, minor modifications or clarifications to the data analysis methods may be described and justified in this document. Any other change to the data analysis methods described in the protocol and the justification for making the change will be described in the CSR. The assumptions for each statistical method may be evaluated. If there is violation of assumptions, alternative statistical methods may be used. Additional exploratory analyses of the data will be conducted as deemed appropriate. The SAP will not be updated to reflect post-hoc analyses conducted after unblinding. These will be described in the study report as appropriate.

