Statistical analysis of this study will be the responsibility of Lilly or its designee. The study PK scientist will be responsible for designing, conducting, and interpreting the PK analysis and delivering PK parameters. The interpretation of final study results will be the responsibility of the clinical research physician (CRP) and the study statistician. These individuals will also be responsible for the appropriate conduct of an internal review process for both the CSR and any study-related material to be authorized for publication by Lilly.

The following general terms will be used globally in the SAP:

- Unless otherwise specified, **summary statistics** stand for n, mean, standard deviation, median, Q3-Q1, minimum, and maximum for continuous variables; and frequency and percentage for categorical variables.
- Study period

- O Dose-limiting toxicity (DLT) assessment period for Part A: for individual patient assessment, period begins on the day of the first study drug dose and ends on the day when the patient:
 - o completed 2 cycles of treatment, or
 - o discontinued from study treatment or study participation before completing 2 cycles due to a DLT.

Note. Two cycles are considered completed on the 14th day from the second dose of ramucirumab.

- o **Study treatment period** begins at the first dose of study treatment and ends when the patient and the investigator agree that the patient will no longer continue any study treatment. The date of this agreement is to be reported on the electronic case report form (eCRF) as the Date of Discontinuation from all study treatment.
- o **30-day short-term follow-up period** begins the day after the patient and the investigator agree that the patient will no longer continue any study treatment and lasts approximately 30 days (± 3 days).
- O Long-term follow-up period begins the day after short-term follow-up is completed and continues every 6 weeks (± 7 days) until progressive disease (PD), thereafter every 3 months (± 7 days) until the patient's death, withdrawal of consent to participate or overall study completion, whichever occurs first.

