5.3.3. Patient-Reported Outcome Analysis Variables

Definitions of variables for PRO analyses are listed below alphabetically.

- Average Symptom Burden Index (ASBI) is calculated as the mean of the 6 symptom items of the LCSS. The ASBI will not be computed for a patient if he/she has one or more missing values for the 6 items. Refer to Section 10.2.1 of the protocol for the definition of the LCSS.
- EQ-5D-5L index score is calculated as recommended by EuroQol (EQ-5D-5L User Guide, www.euroqol.org). Index score and visual analog scale (VAS) will be calculated for each assessment period as per current recommendations (van Hout et al. 2012). The index score is calculated from a set of item weights to derive a score of -0.285 to 1, with 1 representing the best health status. United Kingdom (UK) weights will be applied for the base case. The index score will not be computed for a patient if he/she has one or more missing values for the 5 items.
- Change from baseline for each LCSS or EQ-5D item at any postbaseline visit is calculated by subtracting baseline assessment result from the current assessment result.
- LCSS total score is calculated as the mean of the 9 LCSS items. The LCSS total score will not be computed for a patient if he/she has one or more missing values for the 9 LCSS items.
- **Maximum change** for each LCSS item is defined as the largest decrease from baseline, which is the smallest (that is, most negative or smallest positive) non-missing value among all change from baseline values.
 - **Note.** Negative values of change from baseline (that is, decreases in the LCSS score towards the lower end of the symptom scale) indicate improvement in symptoms. For a patient and given LCSS item, if all change values are positive, the smallest positive change will be the maximum change; if at least one change value is negative, the most negative value will be the maximum change.
- Time to deterioration (TtD) for each of the 9 LCSS items, ASBI, and the LCSS total score is defined as the time from the date of randomization until the date of the first ≥15-mm increase from baseline (de Marinis et al. 2008). Alternative definitions of minimally important differences may be explored as needed. Patients without deterioration will be censored on the date of the patient's last postbaseline LCSS assessment for this item or randomization date, whichever is last.

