Compliance for the PRO instruments will be reported for the ITT population. All other PRO analyses will be on the ITT population and will include those from whom a completed PRO instrument was obtained at baseline and at least one postbaseline (either during study treatment period or 30-day short-term postdiscontinuation follow-up period); thus, the actual patients included for each analysis will depend on the instrument and response variable.

A patient listing of analysis population details will be provided. This listing will be presented by treatment arm and will include: investigator site, patient identifier, inclusion/exclusion flag for each population, and reason for exclusion from each population. All patients screened will appear on this listing.

Part C ITT Population: All patients who will be enrolled to study treatment during Part C. ITT population will be used for demographic, baseline disease characteristics, and 1-year PFS rate and PFS2.

Part C Period 1 Safety Population: All enrolled patients who received at least 1 dose of any study treatment in Part C Period 1.

Part C Period 2 Safety Population: All enrolled patients who received at least 1 dose of any study treatment in Part C Period 2.

The Part C safety populations will be used for all dosing/exposure, AEs, and resource utilization analyses. The safety summaries may be provided by period.

Pharmacodynamic and/or tailoring biomarker analyses will be based on the subset ITT population in Part C from whom a valid assay result (according to laboratory guideline) has been obtained.

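### LCSS maximum improvement is each patient's best value over an observation period tied to time on treatment, yet the arms are tested on it; longer PFS alone can produce a small p-value (minor, supportive analysis)

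*SAP*

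**What the plan says.** Section 5.13.1 defines maximum improvement as the largest decrease from baseline for each LCSS item, the ASBI and the total score, which makes 9 + 1 + 1 = 11 scores. It then prescribes a comparison: "The analysis of maximum improvement will be conducted to compare the study treatment arms for each score using analysis of covariance". The model adjusts for nothing but the baseline value, and a Mann-Whitney-Wilcoxon test is added. Section 5.3.3 defines the corresponding item-level variable as the smallest "non-missing value among all change from baseline values". Neither section limits the values to a period common to both arms.

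The observation period is set patient by patient. Section 5.7.1 includes in the PRO analyses patients with a completed instrument at baseline and "at least one postbaseline (either during study treatment period or 30-day short-term postdiscontinuation follow-up period". Section 5.2 makes the length of treatment an individual matter, since it "begins at the first dose of study treatment and ends when the patient and the investigator agree that the patient will no longer continue"; the synopsis in Section 1 continues treatment to progression, unacceptable toxicity or another permitted reason.

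On status, Section 5.13 says "Descriptive analyses with each PRO instrument will be performed for Parts B and C". Section 5.2, however, gives a default for Part B: "All tests of treatment effects will be conducted at a two-sided alpha level of 0.05" unless otherwise stated, and Section 5.13.1 states nothing else for these two tests.

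**The concern.** The variable is a per-patient minimum over however many assessments that patient happens to have. With visit-to-visit noise, the minimum of more values is lower on average even if the symptom process is identical. Time on treatment is tied to progression, the event that ramucirumab is designed to delay, so the arm with longer PFS tends to contribute more values per patient. Neither ANCOVA on baseline nor Mann-Whitney-Wilcoxon accounts for number of assessments or time observed. The bias therefore appears when the trial succeeds on its primary endpoint, and it favours the experimental arm.

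At stake is a small p-value on one of 11 scores being read as symptom benefit when it partly reflects longer observation. The stakes are low: Section 5.13.1 uses LCSS primarily for time to deterioration (TtD), and no PRO endpoint is in the PFS–OS testing hierarchy of Section 5.11.2.1.

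**Working it through.** **1. The plan's own figures (SAP 5.1.2).** These are 270 PFS events, HR 0.71, one-sided alpha 0.02499 and a placebo median of 11 months.
- Schoenfeld power: √270/2 × |ln 0.71| − 1.960 = 8.216 × 0.3425 − 1.960 = 0.854, so power is Φ(0.854) = 80.3%. The plan says at least 80%.
- Median gain under exponential PFS: 11/0.71 − 11 = 15.49 − 11 = 4.49 months. The plan says "the HR of 0.71 amounts to an approximate 4.5-month improvement in median PFS for the ramucirumab plus erlotinib arm".

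Both reproduce. The SAP gives no operating figure for the maximum-improvement test.

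**2. Simulation inputs.**
- From the SAP: 225 patients per arm, exponential PFS with medians 11 and 15.49 months, cut-off at the 270th PFS event, two-sided 5%.
- Assumed, because the SAP gives none of these: uniform accrual over 24 months; LCSS SD 20 mm; exchangeable within-patient correlation 0.4, 0.6 or 0.8 (at 0.6 the within-patient SD is 20 × √0.4 = 12.6 mm); assessment every 2 or 6 weeks on treatment plus one visit about 30 days after stopping; drift of 0, 1 or 2 mm/month, the same in both arms.
- Outcome: minimum post-baseline value minus baseline. There is no treatment effect on symptoms.
- 4000 trials per setting; Monte Carlo SE at 5% is √(0.05 × 0.95/4000) = 0.3 points.

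**3. Exposure when time on treatment follows PFS (placebo vs ramucirumab).** Mean time on treatment is 10.4 vs 12.1 months. Mean assessments per patient are 7.7 vs 8.8 (6-weekly) or 22.8 vs 26.4 (2-weekly).

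**4. Rejection rates with no symptom effect.**

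| Setting | ANCOVA | Mann-Whitney | Spurious shift |
|---|---|---|---|
| Flat symptoms | 12–17% | 11–12% | 0.8–1.5 mm |
| Worsening 1 mm/month | 7–9% | 6–8% | 0.4–0.9 mm |
| Worsening 2 mm/month | 6–7% | 5–7% | 0.2–0.6 mm |
| Scores floored at 0, flat | 13–14% | 8–10% | – |
| Scores floored at 0, 1 mm/month | 7–9% | 6–7% | – |
| Toxicity stopping nearly equalises exposure | about 5% | about 5% | – |
| Control: PFS HR 1 | 4.7–5.6% | 4.6–5.7% | – |

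With flat symptoms, 97–99% of the ANCOVA rejections favour ramucirumab. The toxicity setting assumes additional stopping rates of 0.005 (placebo) and 0.02 (ramucirumab) per month, which gives mean exposure of 10.0–10.1 vs 10.3 months. The floor runs use a mean of 30 with values clipped to 0–100, with and without an early 5-mm improvement in both arms. The toxicity and floor runs use correlation 0.6.

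The HR 1 control returns to nominal, so the excess comes from unequal exposure and not from the tests themselves.

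**5. Different noise model.** A separate simulation (600 trials per scenario) used AR(1) correlation 0 to 0.8, within-patient SD 5–15 mm, visits every 2, 4 or 6 weeks, a 36-month cut-off, and no drift or toxicity stopping. ANCOVA rejected in 13–24% and Mann-Whitney in 9–20% of trials. With follow-up never cut off, the figures were 20–38% and 13–32%. These are upper-end cases. They confirm the direction and should not be used to raise the estimate in step 4.

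**The case against.** The strongest reply is that the size rests on inputs the SAP does not supply. The upper figures need symptoms that stay flat until progression; with steady worsening the excess shrinks to a few points. If toxicity ends treatment earlier on ramucirumab, exposure may be nearly equal and the excess disappears. This stands: from the SAP alone the inflation could be noticeable or nil. Serial correlation does not settle the matter. With AR(1) 0.8 and flat symptoms, different runs gave ANCOVA/Mann-Whitney rates as low as 9%/7% and others of 17%/14% and above.

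Second, the PRO analyses are called descriptive, and 11 scores by two tests at an unadjusted 5% could not be confirmatory anyway. This keeps the point minor. It does not make the tests valid, and if the intent is descriptive then dropping the p-values is the consistent course.

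Third, best improvement while under observation can legitimately include a longer opportunity to improve. That holds for real late improvement. The simulated excess, however, arises with no treatment effect on symptoms.

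Fourth, Section 5.7.1 states which patients are included, not which values enter the maximum, so the treatment period plus 30 days is an inference. That is fair, but the argument does not need it: Section 5.3.3 takes all values without limit.

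Finally, TtD and the mixed model for repeated measures (MMRM) also face treatment-related dropout. That is true, and Section 5.13.1 already foresees a possible pattern-mixture sensitivity analysis. Neither takes an extreme over unequal observation time.

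**Conclusion.** The concern holds as a minor point. The plan's own definition favours the longer-observed arm, and the plan tests the arms on it without adjustment. At the design HR of 0.71, with no symptom effect, the false-positive rate of the nominal 5% tests is about 5–17% for ANCOVA and 5–12% for Mann-Whitney in the main set of simulations. The low end applies if toxicity stopping equalises exposure, the high end if symptoms are flat and time on treatment follows PFS. The direction is firm wherever exposure differs. The size is uncertain because LCSS schedule, variance, correlation and trajectory are all assumed. The spurious shift of 0.2–1.5 mm is at most 1.5/15 = one tenth of the 15-mm deterioration threshold in Section 5.3.3, so the harm is a misleading p-value and not a large apparent effect.

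**What to change.** In Section 5.13.1, state that LCSS maximum improvement is summarised descriptively by arm without between-arm p-values, and that between-arm LCSS inference comes from TtD and from the planned MMRM at pre-stated visits. This costs one sentence and minor programming, and loses no data.

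If a test is wanted, compute maximum improvement in Sections 5.3.3 and 5.13.1 over one fixed early window common to both arms. In the simulation about 12 weeks gave 5–6% (ANCOVA) and about 5% (Mann-Whitney). A 24-week window removed only part of the bias (6–8% and 5–6%). The 12-week window has a cost: about 1.9 values per patient if assessed 6-weekly, a question that becomes best early improvement, and a residual shift of 0.2–0.3 mm because early stoppers still have fewer values. Descriptive reporting is therefore preferable.

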5.6. Adjustments for Covariates

As supportive analysis, the primary PFS and secondary efficacy endpoint OS of Part B will also be analyzed adjusting for prespecified potential prognostic factors chosen from the variables listed below, with * indicating the reference level. Detailed description as for which factors to be used will be provided for relevant analyses in later sections.

- Randomization stratification factors:
 - o EGFR mutation (exon 19 deletion or exon 21 [L858R] substitution mutation*)
 - o Gender (male or female*)
 - o Region (East Asia or other*)
 - o *EGFR* testing method (*Therascreen*[®] [Qiagen] and *Cobas*[®] [Roche] or other PCR and sequencing-based methods*)
- Other factors of interest:
 - o age (<65 years or ≥ 65 years*)
 - o age (<70 years or ≥ 70 years*)
 - o age (<75 years vs. ≥ 75 years)
 - smoking history (ever or never smoker*)

Note. The definition of "ever smoker" includes those who smoked ≥100 cigarettes, cigars, or pipe-fulls in his/her lifetime and the definition of "never smoker" is one who smoked <100 cigarettes, cigars, or pipe-fulls in his/her lifetime

- o performance status (0 or 1*)
- o initial stage at diagnosis (Stage IV or other)
- o liver metastases (yes vs no)

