5.11.1. Primary Efficacy Analyses

The primary efficacy analysis will be performed in the Part B ITT population. For the primary comparison of investigator-assessed PFS between the 2 assigned study treatment arms, a stratified log-rank test at alpha level of 0.04998 (2-sided) will be performed to test the following statistical hypotheses about the PFS HR for ramucirumab plus erlotinib over placebo plus erlotinib:

 H_0 : PFS $HR \ge 1.00$

H_a: PRS HR < 1.00

The stratification will be the same as that used for randomization in the IWRS. An unstratified log-rank test will also be performed.

The following analyses of PFS will also be performed:

- Summary of PFS events (number and percentage), censoring rate, and reasons for censoring
- Kaplan-Meier survival curve (Kaplan and Meier 1958) by treatment arm will be provided.
- Restricted mean difference in PFS between the treatment arms and its 95% CI, while the
 restriction time is defined by the latest time where the standard error of the PFS estimates
 are ≤ 0.075 months.
- The Kaplan-Meier method will be used to estimate parameters (medians, quartiles, and percentages), difference of percentages and associated 95% CI and p-values for landmark analyses on each treatment group at 3 month intervals, based on a normal approximation. Patients who did not have the event at the corresponding time point will be considered right-censored observations.
- HR for treatment effect will be estimated using Cox proportional hazards (PH) model (Cox 1972) stratified identically to the primary log-rank test with assigned treatment as the only covariate, reported with 2-sided 95% CIs. All randomized patients, according to the ITT principle, will be included in the analysis of this endpoint. This Cox PH model will be referred to as the primary Cox PH model henceforth.

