5.11.3. Exploratory Efficacy Analyses

Time to deterioration in ECOG PS and its variations will be analyzed using the Kaplan-Meier method and compared using an unstratified log-rank test. The association between PFS event and ECOG PS deterioration will be assessed through an analysis of change from baseline in ECOG PS by objective progression (yes versus no) by tumor measurement period.

Time to diagnosis of CNS metastases will be analyzed using the Kaplan-Meier method and compared using an unstratified log-rank test for Part B only. For Part C, time to diagnosis of CNS metastases will be analyzed using the Kaplan-Meier method.

A waterfall plot of the (best) percent change from baseline in target lesion measurement will be generated for each study arm in Part B and Part C period 1.

Regarding PFS2 in Part B and PFS in Part C Period 2, the median with 95% CI, and progression free survival rates at various time points will be estimated using Kaplan-Meier method (Kaplan and Meier 1958).

A 1-year PFS rate of Part C, i.e., a cumulative proportion of patients who survived during the first year (that is, 1 year from enrollment) in the study without disease progression, will be estimated using Kaplan-Meier method (Kaplan and Meier 1958) in addition to PFS curves, the median with 95% CI, and survival rates at various time points, for Part B and C, respectively.

For PFS2 and OS in Part C Period 2, the median with 95% CI will be estimated using Kaplan-Meier method (Kaplan and Meier 1958) for patients that receive osimertinib after disease progression.

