5.13.2. EuroQol EQ-5D-5L: Health State Utilities

Summary statistics for the index and VAS will be calculated for each assessment period by treatment arm. The EQ-5D 5L responses for each item will be summarized by frequency and corresponding percentages by treatment arm. Mean change from baseline will be estimated for the EQ-5D-5L index value and the EQ VAS self-rated health score using longitudinal MMRM regression models and will include independent variables treatment, visit, treatment*visit, and baseline. A negative change from baseline will indicate improvement.

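### The LCSS and EQ-5D-5L mean-change models and the LCSS maximum-improvement ANCOVA leave out the randomization stratification factors: a possible small, conservative loss of precision that costs nothing to remove

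*SAP*

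**What the plan says.** SAP Section 5.6 lists four two-level items under "Randomization stratification factors": EGFR mutation type, gender, region and EGFR testing method. For the primary PFS log-rank test, Section 5.11.1 states "The stratification will be the same as that used for randomization in the IWRS", and the primary Cox model follows the same stratification. Section 5.11.2.1 carries the PFS methods over to OS. Section 5.11.2.2 compares ORR and DCR with a Cochran-Mantel-Haenszel test that adjusts for the stratification variables.

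The patient-reported outcomes are treated in two ways. In Section 5.13.1, "The LCSS assessments will be used primarily to calculate TtD for each of the 9 items, ASBI, and LCSS total score", and the hazard ratios for that endpoint come from a Cox model stratified in the same way as the stratified log-rank tests. The other LCSS comparisons do not use the factors. Maximum improvement is compared by "analysis of covariance (using only baseline score as a covariate") together with a Mann-Whitney-Wilcoxon test, and the repeated-measures model for mean change "will include independent variables treatment, visit, treatment*visit, and baseline". Section 5.13.2 analyzes the EQ-5D-5L index and VAS "using longitudinal MMRM regression models and will include independent variables treatment, visit, treatment*visit, and baseline".

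On status, Section 4.2 makes the comparison of patient-reported outcomes between arms a secondary objective of Part B. Section 5.13 calls the analyses of these instruments descriptive. Section 5.2 sets a two-sided 0.05 level for tests of treatment effects in Part B unless stated otherwise.

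**The concern.** Stratified randomization holds the arms close to balance on the four factors. If those factors are related to the outcome, balance removes their contribution from the true variability of the treatment difference. A linear model without them still leaves their variance in the residual, so it reports a standard error larger than the true one. Confidence intervals are then too wide, tests run below their nominal level, and some power is given up.

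At stake are the precision and calibration of three sets of secondary comparisons: LCSS mean change, LCSS maximum improvement, and EQ-5D-5L index and VAS change. The SAP gives no reason for the omission, whereas Section 5.5 does explain why investigative center is left out of adjusted models. The factors are already recorded and already used for other endpoints, including another analysis of the same LCSS data.

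**Working it through.** **The plan's own figure.** The SAP states no power or precision for the LCSS or EQ-5D-5L analyses. Its only Part B power figure is for PFS (Section 5.1.2: 270 events, HR 0.71, one-sided 0.02499, at least 80%). By the Schoenfeld formula, Φ(½√270 × |ln 0.71| − 1.960) = Φ(2.814 − 1.960) = Φ(0.854) = 80.3%. It reproduces, but it does not bear on this point.

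**Inputs.** From the SAP: the model terms (5.13.1, 5.13.2), the four factors (5.6) and the two-sided 0.05 level (5.2). Assumed: R², the share of outcome variance left after baseline that the four factors explain. The SAP gives no value, so a range is shown. Also assumed: the analysed set keeps the balance created by randomization.

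**Formulas.** Let σ² be the residual variance without the factors. Under balance, the true variance of the treatment difference is proportional to (1 − R²)σ², while the planned model reports one proportional to σ².

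- Reported SE / true SE = 1/√(1 − R²)
- True two-sided size = 2 × [1 − Φ(1.96/√(1 − R²))]
- Power of the planned test, for an effect that the adjusted test detects with 80% power = Φ(2.8016 − 1.96/√(1 − R²)), where 2.8016 = 1.9600 + 0.8416

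| Assumed R² | SE ratio | 1.96 × ratio | True size | Power (adjusted test: 80%) |
|---|---|---|---|---|
| 0 | 1.0000 | 1.960 | 5.0% | 80.0% |
| 2% | 1.0102 | 1.980 | 4.8% | Φ(0.822) = 79.4% |
| 5% | 1.0260 | 2.011 | 4.4% | Φ(0.791) = 78.5% |
| 10% | 1.0541 | 2.066 | 3.9% | Φ(0.736) = 76.9% |

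At an R² of 20% the standard error would be 11.8% too large and power 72.9%.

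**Does the same reasoning reach the ECOG analysis?** Section 5.11.3 says "Time to deterioration in ECOG PS and its variations will be analyzed using the Kaplan-Meier method and compared using an unstratified log-rank test". The formulas above are for linear models and do not apply to a log-rank test, so this was simulated. The set-up was 450 patients, permuted blocks of 4 within 2⁴ = 16 cells (450/16 ≈ 28 patients per cell) and 3,000 runs; factor prevalences, event rates and treatment effects were assumed. Power of the unstratified against the 16-stratum log-rank test, by assumed hazard ratio per factor:

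| HR per factor | Low-event setting (about 68 to 163 events) | High-event setting (about 229 to 362 events) |
|---|---|---|
| 1.0 | 56.5% vs 54.6% | 75.0% vs 73.0% |
| 1.15 | 65.6% vs 64.3% | 80.0% vs 78.8% |
| 1.3 | 76.1% vs 75.4% | 83.0% vs 82.0% |
| 1.6 | 88.3% vs 88.9% | 83.4% vs 88.0% |

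Up to moderate prognostic strength the planned unstratified test does as well or 1 to 2 points better. A separate simulation (2,000 runs, with its own assumed event rates and treatment effects) compared it with a Cox model carrying the four factors as covariates. With hazard ratios per factor of 1.0, 1.15, 1.3 and 1.6, unstratified against adjusted power was 35.2 vs 34.7%, 43.4 vs 43.1%, 53.3 vs 53.9% and 66.2 vs 69.8% with few events. With many events it was 62.3 vs 62.3%, 65.8 vs 66.8%, 71.8 vs 74.8% and 70.9 vs 79.9%. Adjustment therefore costs almost nothing, and its larger gains appear when the factors are strong.

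**The case against.** The strongest reply is that little depends on these models. The main LCSS analysis, time to deterioration, is already stratified; the repeated-measures model is an addition to it. Section 5.13 calls the patient-reported analyses descriptive, and they lie outside the PFS-then-OS testing sequence of Section 5.11.2.1. All three models already contain the baseline score, which may absorb most of what the factors could explain. Any error is conservative. The covariates are stated without ambiguity, so the plan does not contradict itself; using different methods for a time-to-event and a mean-change summary is not in itself an inconsistency.

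There is also a technical reply. Section 5.7.1 limits these analyses to patients with a completed baseline instrument and at least one later one, and Section 5.4 does not impute missing values. Balance on the factors may weaken over visits, so the sizes in the table describe the balanced case.

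Most of this stands, and it limits the weight of the point. It does not remove it. Comparing these outcomes between arms is a secondary objective, and the ANCOVA is planned expressly as a comparison of arms. If balance were lost altogether, the size would return to 5% but the efficiency loss would remain: at R² = 10%, power would be Φ(2.8016 × √0.90 − 1.96) = Φ(0.698) = 75.7%.

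A reader might go further and infer that every LCSS analysis ignores the stratification, that power is certainly lost, or that the unstratified ECOG test is an error. The documents support none of these. The LCSS Cox model is stratified, the loss depends on an R² that the SAP does not give, and the unstratified test avoids sparse strata for an endpoint that Section 4.3 lists as exploratory.

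**Conclusion.** The point holds as a minor one, for three analyses: the LCSS repeated-measures model, the LCSS maximum-improvement ANCOVA and the EQ-5D-5L repeated-measures model. If the factors predict patient-reported change beyond baseline, with R² between 2% and 10%, the loss is about 0.6 to 3 power points. If they do not, there is no loss. The result rests on the assumed R² and, for the sizes, on the analysed set keeping the randomized balance. The omission is conservative: it does not inflate type I error, and the PFS and OS conclusions are untouched. The LCSS time-to-deterioration model needs no change, and the ECOG log-rank test is a defensible choice.

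**What to change.** In Sections 5.13.1 and 5.13.2, add EGFR mutation, gender, region and EGFR testing method, using the IWRS values, as fixed main effects to the LCSS and EQ-5D-5L repeated-measures models and to the LCSS maximum-improvement ANCOVA. Main effects are enough; the 16-cell cross-classification is not needed. Make the change before the aggregate database is unblinded, which Section 5.2 allows for minor modifications described and justified in the SAP.

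For time to deterioration in ECOG performance status, keep the unstratified log-rank test. A Cox model with the four factors as covariates may be added as an optional supportive analysis.

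The cost is a wording change and four model terms that are already in the database. No further data, patients or follow-up are needed.
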